7.5.7 Vital Signs and Physical Examination

Vital sign measurements will be presented for each subject in a data listing. Systolic blood pressure, diastolic blood pressure, heart rate, respiration rate, and temperature will be summarized as actual value and change from Baseline by visit.

All physical examination findings will be presented in a data listing.

7.5.8 Medical History

A by-subject data listing of medical history will be presented. Medical history will be coded using MedDRA v23.0 or higher, and the number and percentage of patients experiencing at least 1 such diagnosis by MedDRA System Organ Class (SOC) and Preferred Term (PT) will be reported.

7.5.9 COVID-19 Issues

By-subject data listings will be provided for COVID-19 test types and results, missed visits and assessments due to COVID-19 specifying reason not done, and adverse events related to COVID-19.

7.6 Handling of Dropouts or Missing Data

To account for missing daily diary entries for WI-NRS and AI-NRS, the average score for a week will be presented, where at least one score or four scores must be collected in a week for the primary and sensitivity analyses, respectively.

No other accommodations will be made for missing data other than those discussed in sections 6.5.7 and 6.5.9.

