12.6 Handling of dropouts or missing data

All available data will be analyzed. The details for any imputations for missing data will be documented in the trial's Statistical Analysis Plan. Subjects who dropout after enrollment but prior to randomization will be replaced.

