6.5.3 Weekly Average WI-NRS and AI-NRS

For WI-NRS and AI-NRS the weekly average is calculated from the daily scores. For the primary analysis the weekly average will be calculated when there is at least one recorded daily score in the corresponding week. Values from study day (as defined above) Day 1 to 7 contributes to Week 1 average, Study Day 8 to 14 to Week 2, etc. Baseline is derived as the average of the daily scores for Day -7 to -1. The average will be derived as the mean of all non-missing values during the respective time period.

Week 1 WI-NRS = (Sum of daily WI-NRS scores from Day 1 to Day 7) / (Total number of WI-NRS diaries entered from Day 1 to Day 7)

Week 2 WI-NRS = (Sum of daily WI-NRS scores from Day 8 to Day 14) / (Total number of WI-NRS diaries entered from Day 8 to Day 14)

Week 3 WI-NRS = (Sum of daily WI-NRS scores from Day 15 to Day 21) / (Total number of WI-NRS diaries entered from Day 15 to Day 21)

Week 4 WI-NRS = (Sum of daily WI-NRS scores from Day 22 to Day 28 or Day of Visit 4 - 1, whichever is earlier) / (Total number of WI-NRS diaries entered from Day 22 to Day 28 or Day of Visit 4 - 1, whichever is earlier)

Week 5 WI-NRS = (Sum of daily WI-NRS scores from Day of Visit 4 to Day of Visit 4 + 6) / (Total number of WI-NRS diaries entered from Day of Visit 4 to Day of Visit 4 + 6)

Week 6 WI-NRS = (Sum of daily WI-NRS scores from Day of Visit 4 + 7 to Day of Visit 4 + 13) / (Total number of WI-NRS diaries entered from Day of Visit 4 + 7 to Day of Visit 4 + 13)

Week 7 WI-NRS = (Sum of daily WI-NRS scores from Day of Visit 4 + 14 to Day of Visit 4 + 20) / (Total number of WI-NRS diaries entered from Day of Visit 4 + 14 to Day of Visit 4 + 20)

Week 8 WI-NRS = (Sum of daily WI-NRS scores from Day of Visit 4 + 21 to Day of Visit 4 + 27 or Day of Visit 5 - 1, whichever is earlier) / (Total number of WI-NRS diaries entered from Day of Visit 4 + 21 to Day of Visit 4 + 27 or Day of Visit 5 - 1, whichever is earlier)

The same conventions are used to calculate Week 1 to Week 8 AI-NRS.

STATISTICAL ANALYSIS PLAN

Version 3.0 12-Jan-22

Week 1 AI-NRS = (Sum of daily AI-NRS scores from Day 1 to Day 7) / (Total number of AI-NRS diaries entered from Day 1 to Day 7)

Week 2 AI-NRS = (Sum of daily AI-NRS scores from Day 8 to Day 14) / (Total number of AI-NRS diaries entered from Day 8 to Day 14)

Week 3 AI-NRS = (Sum of daily AI-NRS scores from Day 15 to Day 21) / (Total number of AI-NRS diaries entered from Day 15 to Day 21)

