7.2.6 Role of Populations in Analyses

The results in the mITT population will be considered definitive for superiority of each active treatment to vehicle with those in the PP population considered supportive. Safety analyses will be performed using the Safety population.

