7.4.1 Analysis of WI-NRS and AI-NRS

The primary endpoint of mean change from Baseline to Week 4 in WI-NRS will be analyzed using analysis of covariance (ANCOVA) models.

In addition, the continuous efficacy endpoints WI-NRS, AI-NRS will be summarized using descriptive statistics at Baseline, Week 1, Week 2, Week 3, Week 4, Week 5, Week 6, Week 7, and Week 8 for actual values and change from Baseline values.

The difference in treatment groups in change from Baseline values at post-baseline visits will be analyzed using a mixed model with repeated measures to account for within subject variability and including visit (Baseline vs. Week 1, Week 2, Week 3, Week 4, Week 5, Week 6, Week 7, Week 8), treatment group, visit-by-treatment interaction, and Baseline value as explanatory variables. The subject variability will be modelled using a compound symmetry covariance matrix. Other types of covariance structure may be applied should they provide a better model fit.

The frequency and rate of WI-NRS and AI-NRS responders at Week 1, Week 2, Week 3, Week 4, Week 5, Week 6, Week 7, Week 8 (\geq 4 point change from Baseline in WI-NRS and AI-NRS) and other responder endpoints (any improvement from Baseline in WI-NRS and AI-NRS, defined as \geq 1 point change from Baseline) will be reported and compared between treatment groups using a logistic regression model by week. Generalized estimating equations to account for repeated measures and within-subject variability may also be applied. Responder status varies by outcome measure, endpoint, and visit. That is, a subject can be considered a responder at one visit, but not the next for a specific measure. Similarly, a subject can be considered a responder for one measure but not another at the same visit.

Additionally, daily WI-NRS and AI-NRS scores will be presented in by-subject data listings.

7.4.2 Analysis of Primary Endpoint of Change from Baseline to Week 4 in Weekly Average WI-NRS

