The ANCOVA model for the primary endpoint change from Baseline to Week 4 in weekly average WI-NRS will have treatment group and Baseline weekly average WI-NRS as explanatory variables. Hypothesis testing will be done using a Dunnett Testing Method, applying pairwise comparisons of each respective B244 dose group to vehicle using a one-sided familywise error rate of 0.10. Treatment effect will be estimated as least squares means using vehicle as reference and adjusted for multiplicity according to the Dunnett Testing Method and presented with one-sided 90% CI.

Additionally, the two B244 dose groups will be compared by presenting the treatment difference estimated using least squares means.

Finally, in a separate analysis, the pooled B244 dose groups will be compared to vehicle using the same ANCOVA model.

STATISTICAL ANALYSIS PLAN

Version 3.0 12-Jan-22

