| | | LSM Difference (SE) | xx.x (xx.xxx) | xx.x (xx.xxx) | xx.x (xx.xxx) | N/A |
| | | 90% UCL Adjusted [5] | XX.X | XX.X | XX.X | N/A |
| | | p-value | X.XXXX | X.XXXX | X.XXXX | N/A |
| | 20.0 v 5.0 | | | | | |
| | | LSM Difference (SE) | N/A | xx.x (xx.xxx) | N/A | N/A |
| | | 90% UCL Adjusted | N/A | XX.X | N/A | N/A |
| | | p-value | N/A | X.XXXX | N/A | N/A |
| | | | | | | |

Table 14.2.2.1 Mean Change in WI-NRS from Baseline to Week 4 - ANCOVA (mITT Population)

[1] CFB = Change from Baseline.

[2] ANCOVA = Analysis of Covariance model.

[3] Model contains treatment group and baseline WI-NRS as explanatory variables, where baseline WI-NRS = (Sum of daily WI-NRS scores from Day -7 to Day -1) / (Total number of WI-NRS diaries entered from Day -7 to Day -1) and at least one WI-NRS daily score is reported between Days -7 and -1. Multiplicity is adjusted for with the Dunnett Testing Method using a one-sided familywise error rate of 0.10. All subjects who meet mITT criteria are included and no data is excluded based on rescue medication use. [4] LSM = Least Squares Mean. SE = Standard Error.

[5] UCL = Upper Confidence Limit for one-sided confidence inteval.

Source: Listing XXXX

PROGRAM NAME: XXXXXXXXXX

DATE: HH:MM/DDMMMYYYY

Programming Note:

Repeat for 14.2.2.2 Mean Change in WI-NRS from Baseline to Week 4 – ANCOVA for PP Population •

• Footnote [3] will be same as in 14.2.2.1, except changing the last statement to "All subjects who meet PP criteria are included."

Table 14.2.2.3.1 Mean Change in WI-NRS from Baseline to Weeks 1 Through 8 – Primary Analysis (mITT Population)

| | | | B244 O.D. 5.0 | B244 O.D. 20.0 | Pooled B244 | Vehicle |
|------------------------|----------------|---------------------|---------------|----------------|---------------|---------------|
| Visit | Statistic Type | Statistic | (N=xx) | (N=xx) | (N=xx) | (N=xx) |
| Week 1 CFB [1] | MMRM [2,3] | n | XX | XX | XX | XX |
| | | LSM (SE) [4] | xx.x (xx.xxx) | xx.x (xx.xxx) | xx.x (xx.xxx) | xx.x (xx.xxx) |
| | | 95% CI | (xx.x, xx.x) | (xx.x, xx.x) | (xx.x, xx.x) | (xx.x, xx.x) |
| | v. Vehicle | LSM Difference (SE) | xx.x (xx.xxx) | xx.x (xx.xxx) | xx.x (xx.xxx) | N/A |
| | | 95% CI | XX.X | XX.X | XX.X | N/A |
| | | p-value | X.XXXX | X.XXXX | X.XXXX | N/A |
| | 20.0 v 5.0 | LSM Difference (SE) | N/A | X.XXXX | N/A | N/A |
| | | 95% CI | N/A | xx.x (xx.xxx) | N/A | N/A |
| Repeat for Weeks 2 – 8 | | p-value | N/A | XX.X | N/A | N/A |

[1] CFB = Change from Baseline.

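### The decisive Week 4 ANCOVA uses observed cases only: earlier diary data go unused, and itch-related loss that differs by arm could shift the estimate either way

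*SAP*

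**What the plan says.** Protocol 12.6 defers the matter: "The details for any imputations for missing data will be documented in the" SAP. SAP 7.6 then states "No other accommodations will be made for missing data other than those discussed in sections 6.5.7 and 6.5.9". Section 6.5.7 imputes medication dates and 6.5.9 adverse-event dates; neither touches an efficacy score.

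The primary model in SAP 7.4.2 "will have treatment group and Baseline weekly average WI-NRS as explanatory variables", tested by Dunnett at a one-sided familywise 0.10. SAP 6.5.3 sets the data requirement: "For the primary analysis the weekly average will be calculated when there is at least one recorded daily score in the corresponding week". SAP 7.2.6 fixes the standing of the result: "The results in the mITT population will be considered definitive for superiority of each active treatment to vehicle". Under 7.2.4, mITT requires one dose and one post-baseline on-site visit, but not a Week 4 score. Note 3 to Table 14.2.2.1 nevertheless reads "All subjects who meet mITT criteria are included and no data is excluded based on rescue medication use".

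Other planned analyses do use earlier diaries or fill gaps:
- The Weeks 1-8 MMRM of SAP 7.4.1 gives a Week 4 contrast. By default, "The subject variability will be modelled using a compound symmetry covariance matrix", although "Other types of covariance structure may be applied should they provide a better model fit". It is read at two-sided 95% (6.3) without multiplicity adjustment (7.4).
- Addendum Section 3 adds a Week 4 ANCOVA with LOCF in all randomized subjects, in answer to an FDA request for analyses covering dropouts with no score. Its table note applies Dunnett at one-sided 0.10.
- Addendum Section 2 adds a WOCF analysis in mITT.

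The Addendum presents both of its analyses as sensitivity analyses.

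**The concern.** One diary entry in the Week 4 window keeps a subject in the primary test. With none, the subject leaves it, even with three full weeks of earlier diaries. The decisive comparison then rests on subjects who still had a score at Week 4.

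If itchier vehicle subjects leave for lack of relief, the vehicle mean looks better than it should, and the shift works against B244 and costs power. If itchier subjects are lost mainly on B244, the shift favours B244 and the 0.10 familywise rate is not held. The information that could reduce either shift is already collected in the Week 1-3 diaries, but the decisive model does not use it.

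**Working it through.** **Inputs from the documents** (SAP 7.1, 7.4.2): 160 evaluable per group, difference 0.65, SD 2.5, Dunnett one-sided 0.10 with two comparisons, 1:1:1, 16.7% dropout before completing the study, 576 enrolled.

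**The plan's own figure.** 160/(1 - 1/6) = 192 per group, and 3 x 192 = 576. It reproduces.

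**Algebra of the shift.** Let d be the share of an arm with no Week 4 score, and g the mean change of missing minus observed subjects. In each arm, observed mean - full mean = -d x g, so the shift in B244 minus vehicle is -(dA x gA - dV x gV).
- 16.7% missing in both arms, gA = 1, gV = 0: -0.167, which overstates B244. Reversed: +0.167.
- Same rate and same gap in both arms: 0.
- Per 1-point between-arm gap: 0.05 at 5% missing and 0.10 at 10%, that is 8% and 15% of 0.65.
- Erasing 0.65 entirely at 16.7% missing would need a gap of 0.65/0.167, about 3.9 points.

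**Effect on the test.** The Dunnett critical value is 1.577 and SE = 2.5 x sqrt(2/160) = 0.2795. Under the null, with both doses shifted in their favour, the threshold becomes 1.577 - shift/0.2795. The familywise error is then 0.138 for a shift of 0.05, 0.185 for 0.10 and 0.262 for 0.167.

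**Simulation.** All trajectories are assumed:
- weekly change SDs 1.6, 2.0, 2.3 and 2.5; correlation 0.85 per lag or 0.80 exchangeable
- baseline SD 1.1, slope -0.3 on change; vehicle mean changes -0.8, -1.3, -1.7 and -2.0
- treatment effect building 25/50/75/100% to Week 4
- Week 1 always observed; dropout logit linear in standardized change
- 'one arm only' means the other arm has the same loss rate, unrelated to itch

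Observed-case shift (150,000 subjects per arm):
- Random loss of 10% v 23.4%: 0.00.
- Same itch-related rule in all arms: 0.00-0.02 under the null; 0.01-0.06 attenuation at a true 0.65.
- One arm only, odds doubling per SD of worse last-observed itch: 0.06-0.07 at 5% loss, 0.10-0.11 at 8%, 0.21-0.24 at 17%.
- In that last scenario the compound-symmetry MMRM keeps 0.03-0.04 at 8% and 0.07 at 17%.

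Rejection for at least one dose (3,000 trials, 192 per arm, correlation 0.85 per lag, 25 imputations; Monte Carlo SE near 0.10 is sqrt(0.1 x 0.9/3000) = 0.005):

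| Scenario | Full data | Observed-case | LOCF | MI |
|---|---|---|---|---|
| Null, random 17% | 0.101 | 0.103 | 0.100 | 0.100 |
| Null, random, B244 23.4% v vehicle 10% | 0.096 | 0.099 | 0.040 | 0.098 |
| Null, random, vehicle 23.4% v B244 10% | 0.096 | 0.086 | 0.185 | 0.091 |
| Null, B244 only, 8% | 0.103 | 0.203 | 0.095 | 0.102 |
| Null, B244 only, 17% | 0.090 | 0.319 | 0.080 | 0.092 |
| Null, B244 only, unseen week, 8% | 0.099 | 0.212 | 0.118 | 0.127 |
| Null, B244 only, unseen week, 17% | 0.107 | 0.380 | 0.141 | 0.167 |
| Effect 0.65, random 8% | 0.938 | 0.924 | 0.927 | 0.933 |
| Effect 0.65, random 17% | 0.933 | 0.890 | 0.898 | 0.910 |
| Effect 0.65, vehicle only, 8% | 0.934 | 0.839 | 0.923 | 0.924 |
| Effect 0.65, vehicle only, 17% | 0.938 | 0.679 | 0.917 | 0.919 |

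A separate simulation on the same assumptions gave B244-only error rates of about 0.16, 0.19 and 0.34 at 5%, 8% and 17% loss.

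**Limit of the MI column.** It keeps everyone randomized, but mITT needs a post-baseline on-site visit. About 35% of the simulated loss falls before Week 2. If all those subjects leave mITT, MI still carries about 0.03 of shift at 8% loss and 0.07-0.08 at 17%. This is an upper case, since some would attend a termination visit.

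**The case against.** The strongest reply is that this was raised and answered. The FDA asked for it, and the Addendum supplies a Dunnett-adjusted LOCF ANCOVA in all randomized subjects. In the table, LOCF does about as well as MI whenever loss is itch-related in one arm, and is slightly closer to 0.10 when loss depends on the unseen week. It fails only when random loss differs by arm (error 0.04 or 0.19), which is where observed-case ANCOVA is sound. Together, the two cover both cases.

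Much of that stands: the gap is in the decisive test, not in the whole plan. But the SAP makes only the observed-case result definitive, and no rule says what follows if LOCF disagrees. Protocol 12.5 names ANCOVA for the primary endpoint; imputing before that same ANCOVA stays within it.

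Several stronger readings are tempting and not supported:
- A reader might infer that about 17% will lack a Week 4 score. The 16.7% covers dropout before study completion, which is Week 8 (Protocol 11.6), and one diary entry in the window is enough. The Week 4 rate within mITT is not stated and may be well below 17%.
- A reader might infer that unequal dropout alone biases the test. Random loss of 10% v 23.4% gives 0.00.
- A reader might set the vehicle-only power of 0.84 and 0.68 against 0.93-0.94 with complete data. The plan already allows for dropout; the fair comparators are 0.92 and 0.89 under random loss at the same rates.
- A reader might expect imputation to remove the shift. Within mITT it does not, because early leavers without an on-site visit are outside the population.

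**Conclusion.** The concern holds in a conditional form. The decisive test discards mITT subjects who have earlier diaries but no Week 4 entry. The estimate is unbiased if, given arm and baseline, having a score is unrelated to itch. A shift of real size needs itch-related loss that differs by arm, and nothing in the documents shows that this will occur or in which direction. The same rule in all arms costs at most 0.06 of attenuation at the planned effect.

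Under the one-arm assumption, the shifts at 5%, 8% and 17% loss are about 9-11%, 15-17% and 32-37% of the planned 0.65, with 17% an upper case. These sizes rest on the assumed trajectories and an odds ratio of 2. The point is a cheap improvement to the primary estimator. It does not show an error in the sample size or the error rate as stated.

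**What to change.** Keep the sentence in SAP 7.6 and add:

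> Exception: for the primary endpoint, a missing Week 4 weekly average WI-NRS is multiply imputed within arm by sequential regression on baseline and Week 1-3 weekly averages (at least 25 imputations). Each data set is analysed by the 7.4.2 ANCOVA, the two dose-vehicle differences and their covariance are combined by Rubin's rules, and each is tested against the Dunnett one-sided 0.10 critical value (about 1.577 at 1:1:1).

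- Name this as primary in mITT. Repeat it in the Addendum ITT population beside LOCF, because mITT cannot recover subjects without a post-baseline on-site visit.
- Keep observed-case ANCOVA, LOCF and WOCF as supportive.
- Add a delta-adjusted analysis that worsens imputed B244 values in steps until the conclusion changes.
- An unstructured MMRM limited to Weeks 1-4 with the same Dunnett adjustment is an acceptable alternative. It is not the same model as the planned Weeks 1-8 MMRM.
- State in the Table 14.2.2.1 note how subjects without a Week 4 score are handled.
- Reconcile Addendum Section 2, which imputes early discontinuers by WOCF only after a TEAE leading to discontinuation, with its table notes, which impute all data missing through dropout.

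The cost is SAP wording and programming on diaries already collected. Alpha, endpoint and mITT stay as planned. Simulated precision is slightly better: mean SE 0.259 v 0.264 at 8% loss, and 0.266 v 0.278 at 17%. The downside is the missing-at-random assumption. If loss depends on the unseen week, roughly 20-30% of the shift remains, and more once pre-Week 2 losses leave mITT.

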7.7 Changes to Planned Analyses

Protocol: PRB244-01 Confidential STATISTICAL ANALYSIS PLAN

Version 3.0 12-Jan-22

With respect to planned analyses in the protocol, the following changes have been made:

- Use of Modified Intent to Treat (mITT) population rather than Intent to Treat (ITT) population. Both populations consist of subjects who are enrolled and apply at least 1 dose of study treatment. mITT population also requires that at least one post-baseline evaluation visit occur.
- Reporting of endpoints for all visits have been added.
- Responder endpoints for EASI and IGA have been added.
- The protocol states that the treatment period is 28 days, yet the IP administration in the Schedule of Assessments covers a 29-day period (Visit 2 to Visit 4). In order to be consistent with the 28-day treatment period, the time frame of Visit 2 to Visit 4-1 will be used to report the following data:
 - NRS rating scores
 - "On-treatment" rescue medication use
 - Dosing diaries for secondary compliance

1 APPENDIX

1.1 **APPENDIX A: Tables**

1.1.1 General

| Display Number | Title | Population | Unique/Repeat |
|----------------|--------------------------------------|--------------|---------------|
| 14.1.1.1 | Subject Enrollment and Disposition | All Subjects | Unique |
| 14.1.1.2 | Analysis Populations and Exclusions | All Enrolled | Unique |
| | | Subjects | |
| 14.1.2.1 | Summary of Major Protocol Deviations | mITT | Unique |
| | (PD)/Violations (PV) | | |
| 14.1.2.2 | Summary of Major Protocol Deviations | Safety | Repeat |
| | (PD)/Violations (PV) | | |
| 14.1.3.1 | Summary of Demographic and Baseline | mITT | Unique |
| | Characteristics | | |
| 14.1.3.2 | Summary of Demographic and Baseline | PP | Repeat |
| | Characteristics | | |
| 14.1.3.3 | Summary of Demographic and Baseline | Safety | Repeat |
| | Characteristics | | |
| 14.1.4.1 | Summary of Baseline Disease Status | mITT | Unique |
| 14.1.4.2 | Summary of Baseline Disease Status | PP | Repeat |
| 14.1.4.3 | Summary of Baseline Disease Status | Safety | Repeat |

| | | B244 O.D. 5.0 | B244 O.D. 20.0 | Pooled B244 | Vehicle | All Subjects |
|--|-----------|---------------|----------------|-------------|-----------|--------------|
| Disposition | Statistic | | | | | |
| Total Number of Subjects | | | | | | |
| Screened | n | | | | | XX |
| Screen Failures [1] | n (%) | | | | | xx (xx.x) |
| Enrolled [2] | n | XX | XX | XX | XX | XX |
| Not Assigned [3,4] | n (%) | | | | | xx (xx.x) |
| Randomized [4] | n (%) | xx (xx.x) | xx (xx.x) | xx (xx.x) | xx (xx.x) | xx (xx.x) |
| Treated [5] | n (%) | xx (xx.x) | xx (xx.x) | xx (xx.x) | xx (xx.x) | xx (xx.x) |
| Completed the Study [6,7] | n (%) | xx (xx.x) | xx (xx.x) | xx (xx.x) | xx (xx.x) | xx (xx.x) |
| Discontinued | n (%) | xx (xx.x) | xx (xx.x) | xx (xx.x) | xx (xx.x) | xx (xx.x) |
| Study Population [8] | | | | | | |
| Safety (SAF) | n (%) | xx (xx.x) | xx (xx.x) | xx (xx.x) | xx (xx.x) | xx (xx.x) |
| Modified Intent-to-Treat (mITT) | n (%) | xx (xx.x) | xx (xx.x) | xx (xx.x) | xx (xx.x) | xx (xx.x) |
| Per Protocol (PP) | n (%) | xx (xx.x) | xx (xx.x) | xx (xx.x) | xx (xx.x) | xx (xx.x) |
| Reason for Early Study Discontinuation | | | | | | |
| Death | n (%) | xx (xx.x) | xx (xx.x) | xx (xx.x) | xx (xx.x) | xx (xx.x) |
| Lost to Follow-up | n (%) | xx (xx.x) | xx (xx.x) | xx (xx.x) | xx (xx.x) | xx (xx.x) |
| Withdrawal of Consent by Subject | n (%) | xx (xx.x) | xx (xx.x) | xx (xx.x) | xx (xx.x) | xx (xx.x) |
| Investigator's Decision | n (%) | xx (xx.x) | xx (xx.x) | xx (xx.x) | xx (xx.x) | xx (xx.x) |
| Adverse Event | n (%) | xx (xx.x) | xx (xx.x) | xx (xx.x) | xx (xx.x) | xx (xx.x) |
| Pregnancy | n (%) | xx (xx.x) | xx (xx.x) | xx (xx.x) | xx (xx.x) | xx (xx.x) |
| Significant Non-Compliance | n (%) | xx (xx.x) | xx (xx.x) | xx (xx.x) | xx (xx.x) | xx (xx.x) |
| Significant Clinical Event | n (%) | xx (xx.x) | xx (xx.x) | xx (xx.x) | xx (xx.x) | xx (xx.x) |
| Incident of Unblinding | n (%) | xx (xx.x) | xx (xx.x) | xx (xx.x) | xx (xx.x) | xx (xx.x) |
| Failure to Meet Continuation Criteria | n (%) | xx (xx.x) | xx (xx.x) | xx (xx.x) | xx (xx.x) | xx (xx.x) |
| Other | n (%) | xx (xx.x) | xx (xx.x) | xx (xx.x) | xx (xx.x) | xx (xx.x) |

Table 14.1.1.1 Subject Enrollment and Disposition (All Subjects)

[1] Percentage based on the number screened.

[2] The number enrolled is equal to the sum of the number randomized and the number not assigned.

[3] Not Assigned includes subjects who passed the initial inclusion/exclusion assessment, but withdrew or were lost-to-follow-up prior to randomization.

[4] Percentage based on the number enrolled.

[5] Percentage based on the number randomized.

[6] Percentage and all subsequent percentages based on the number treated.

[7] Completed the Study indicates completion up to and including Week 8 visit.

[8] Safety Population: All subjects treated with at least 1 dose of IP.Modified Intent-to-Treat Population: All randomized participants who apply at least 1 dose of IP and have at least one post-baseline evaluation visit.

Per Protocol Population: Includes all subjects in the mITT population who administered at least 50% of IP (based on the weight of IP used calculated using the algorithm: difference in weight of all bottles dispenced and weight of all bottles returned must be at least 50% of the initial theoretical product weight i.e.(0.14 g per pump x 20 pumps per day x 28 days = 78.4 g)), have completed their Week 4 visit and did not have any major protocol deviations. Source: Listing XXXX

PROGRAM NAME: XXXXXXXXXX

DATE: HH:MM/DDMMMYYYY

Programming Note:

• Reason for Early Study Discontinuation response "Significant Clinical Event" corresponds to the CRF response "Any clinical AE, lab abnormality, or other medical condition or situation occurs such that continued participation in the study would not be in the best interest of the subject."

Table 14.1.1.2 Analysis Populations and Exclusions (All Enrolled Subjects)

| | | B244 O.D. 5.0 | B244 O.D. 20.0 | Pooled B244 | Vehicle | All Subjects |
|---|-----------|---------------|----------------|-------------|-----------|--------------|
| Number of Subjects | Statistic | | | | | - |
| Enrolled | n | XX | XX | XX | XX | XX |
| Randomized [1] | n (%) | xx (xx.x) | xx (xx.x) | xx (xx.x) | xx (xx.x) | xx (xx.x) |
| Included in Safety (SAF) [2,4] | n (%) | xx (xx.x) | xx (xx.x) | xx (xx.x) | xx (xx.x) | xx (xx.x) |
| Excluded from Safety (SAF) | n (%) | xx (xx.x) | xx (xx.x) | xx (xx.x) | xx (xx.x) | xx (xx.x) |
| No IP Applied | n (%) | xx (xx.x) | xx (xx.x) | xx (xx.x) | xx (xx.x) | xx (xx.x) |
| Included in Modified Intent-to-Treat (mITT) [3,5] | n (%) | xx (xx.x) | xx (xx.x) | xx (xx.x) | xx (xx.x) | xx (xx.x) |
| Excluded from Modified Intent-to-Treat (mITT) | n (%) | xx (xx.x) | xx (xx.x) | xx (xx.x) | xx (xx.x) | xx (xx.x) |
| No Post-Baseline Evaluation Visit | n (%) | xx (xx.x) | xx (xx.x) | xx (xx.x) | xx (xx.x) | xx (xx.x) |
| Included in Per Protocol (PP) [6] | n (%) | xx (xx.x) | xx (xx.x) | xx (xx.x) | xx (xx.x) | xx (xx.x) |
| Excluded from Per Protocol (PP) | n (%) | xx (xx.x) | xx (xx.x) | xx (xx.x) | xx (xx.x) | xx (xx.x) |
| Major Protocol Deviation | n (%) | xx (xx.x) | xx (xx.x) | xx (xx.x) | xx (xx.x) | xx (xx.x) |
| Did Not Complete Week 4 Visit | n (%) | xx (xx.x) | xx (xx.x) | xx (xx.x) | xx (xx.x) | xx (xx.x) |
| Applied < 50% IP | n (%) | xx (xx.x) | xx (xx.x) | xx (xx.x) | xx (xx.x) | xx (xx.x) |

[1] Percentage based on number enrolled.

[2] Percentage based on the number randomized.

[3] Percentage and all subsequent percentages based on the number treated.

[4] Safety Population: All subjects treated with at least 1 dose of IP.

[5] Modified Intent-to-Treat Population: All randomized participants who apply at least 1 dose of IP and have at least one post-baseline evaluation visit.

[6] Per Protocol Population: Includes all subjects in the mITT population who administered at least 50% of IP (based on the weight of IP used calculated using the algorithm:

difference in weight of all bottles dispenced and weight of all bottles returned must be at least 50% of the initial theoretical product weight i.e.(0.14 g per pump x 20 pumps per day x 28 days = 78.4 g)), have completed their Week 4 visit and did not have any major protocol deviations.

Source: Listing XXXX

PROGRAM NAME: XXXXXXXXX

DATE: HH:MM/DDMMMYYYY

Table 14.1.2.1 Summary of Major Protocol Deviations (PD) / Violations (PV) (Modified Intent-to-Treat Population)

| | | B244 O.D. 5.0 | B244 O.D. 20.0 | Pooled B244 | Vehicle |
|--|-----------|---------------|----------------|-------------|-----------|
| | Statistic | (N=xx) | (N=xx) | (N=xx) | (N=xx) |
| Subjects with At Least One Major PD/PV [1,2] | n (%) | xx (xx.x) | xx (xx.x) | xx (xx.x) | xx (xx.x) |
| PD/PV Category 1 | n (%) | xx (xx.x) | xx (xx.x) | xx (xx.x) | xx (xx.x) |
| PD/PV Category 2 | n (%) | xx (xx.x) | xx (xx.x) | xx (xx.x) | xx (xx.x) |
| PD/PV Category 2 | n (%) | xx (xx.x) | xx (xx.x) | xx (xx.x) | xx (xx.x) |
| etc. | | | | | |

[1] Percentage and all subsequent percentages based on the number treated.
[2] Subjects are counted once per PD/PV category experienced.
Source: Listing XXXX
PROGRAM NAME: XXXXXXXXX

DATE: HH:MM/DDMMMYYYY

Programming Note:

• Repeat for 14.1.2.2 Summary of Major Protocol Deviation (PD) / Violations (PV) for Safety Population

| | | B244 O.D. 5.0 | B244 O.D. 20.0 | Pooled B244 | Vehicle |
|---|-----------|---------------|----------------|--------------|--------------|
| | Statistic | (N=xx) | (N=xx) | (N=xx) | (N=xx) |
| Age [1] | | | | | |
| 18 to 40 years | n (%) | xx (xx.x) | xx (xx.x) | xx (xx.x) | xx (xx.x) |
| 41 to 54 years | n (%) | xx (xx.x) | xx (xx.x) | xx (xx.x) | xx (xx.x) |
| 55 to 65 years | n (%) | xx (xx.x) | xx (xx.x) | xx (xx.x) | xx (xx.x) |
| Age | n | XX | XX | XX | XX |
| | Mean (SD) | xx.x (xx.xx) | xx.x (xx.xx) | xx.x (xx.xx) | xx.x (xx.xx) |
| | Median | XX.X | XX.X | XX.X | XX.X |
| | Min, Max | XX, XX | XX, XX | XX, XX | XX, XX |
| Sex | | | | | |
| Male | n (%) | xx (xx.x) | xx (xx.x) | xx (xx.x) | xx (xx.x) |
| Female | n (%) | xx (xx.x) | xx (xx.x) | xx (xx.x) | xx (xx.x) |
| Ethnicity | | | | | |
| Hispanic or Latino | n (%) | xx (xx.x) | xx (xx.x) | xx (xx.x) | xx (xx.x) |
| Not Hispanic or Latino | n (%) | xx (xx.x) | xx (xx.x) | xx (xx.x) | xx (xx.x) |
| Race | | | | | |
| American Indian or Alaskan Native | n (%) | xx (xx.x) | xx (xx.x) | xx (xx.x) | xx (xx.x) |
| Asian | n (%) | xx (xx.x) | xx (xx.x) | xx (xx.x) | xx (xx.x) |
| Black or African American | n (%) | xx (xx.x) | xx (xx.x) | xx (xx.x) | xx (xx.x) |
| Native Hawaiian or Other Pacific Islander | n (%) | xx (xx.x) | xx (xx.x) | xx (xx.x) | xx (xx.x) |
| White | n (%) | xx (xx.x) | xx (xx.x) | xx (xx.x) | xx (xx.x) |
| Other | n (%) | xx (xx.x) | xx (xx.x) | xx (xx.x) | xx (xx.x) |
